2. STUDY DESIGN

Enrolment of
800 toddlers

Randomisation
(1:1:1:1)

- **Experimental design:** Phase 3, open-label, randomized, controlled, multicenter study with 4 parallel vaccine groups.
- **Duration of the study:** 62 months for each subject:
 - Epoch 001: Primary starting at Visit 1 (Month 0) and ending at the phone contact (Month 9)
 - Epoch 002: Persistence Visit 5 ending Year 1
 - Epoch 003: Persistence Visit 6 ending Year 3
 - Epoch 004: Persistence Visit 7 ending Year 5
- **Control:** Active control.
- **Vaccine allocation:** Randomized.
- **Blinding:** Open-label.

- The subsets that are used for antibody titer determination are given below:

Subset name	Description	Definition
Subset 1	Vaccine groups ACWY1d and ACWY2d: hSBA-MenA and hSBA-MenC	The first 50% of enrolled subjects within each country (according to their enrollment date) for vaccine groups ACWY1d and ACWY2d will be tested for hSBA-MenA and hSBA-MenC at all blood sampling time points planned for each vaccine group (ie, Visits 1, 2, 5, 6, and 7 for the ACWY1d vaccine group and Visits 1, 2, 4, 5, 6, and 7 for the ACWY2d vaccine group).
Subset 2	Vaccine groups ACWY1d and ACWY2d: hSBA-MenW-135 and hSBA-MenY	The remaining 50% of enrolled subjects within each country (according to their enrollment date) for vaccine groups ACWY1d and ACWY2d will be tested for hSBA-MenW-135 and hSBA-MenY at all blood sampling time points planned for each vaccine group (ie, Visits 1, 2, 5, 6, and 7 for the ACWY1d vaccine group and Visits 1, 2, 4, 5, 6, and 7 for the ACWY2d vaccine group).
Subset 3	Vaccine groups Co-ad and PCV13: OPA 3, 4, 6B, 14, and 23F	The first 50% of enrolled subjects within each country (according to their enrollment date) for vaccine groups Co-ad and PCV13 will be tested for opsonophagocytic activity (OPA) for pneumococcal serotypes 3, 4, 6B, 14, and 23F at Visits 1 and 2.
Subset 4	Vaccine groups Co-ad and PCV13: OPA 1, 5, 6A, 7F, 9V, 18C, 19A, and 19F	The remaining 50% of enrolled subjects within each country (according to their enrollment date) for vaccine groups Co-ad and PCV13 will be tested for OPA for pneumococcal serotypes 1, 5, 6A, 7F, 9V, 18C, 19A, and 19F at Visits 1 and 2.

The following vaccine group names will be used for the statistical analyses:

Vaccine group order in tables	Vaccine group label in tables	Vaccine group definition for footnote	Pooled vaccine groups label in tables	Pooled definition for footnote
1	ACWY1d	Subjects who received 1 dose of MenACWY-TT at Month 0	Pool1d	Subjects receiving MenACWY-TT at Month 0 only or at Month 0 and Month 2
2	ACWY2d	Subjects who received 2 doses of MenACWY-TT at Month 0 and Month 2	Pool1d	Subjects receiving MenACWY-TT at Month 0 only or at Month 0 and Month 2
3	Co-ad	Subjects who received 1 dose of MenACWY-TT and 1 dose of Prevenar 13 at Month 0		
4	PCV13	Subjects who received 1 dose of Prevenar 13 at Month 0 and 1 dose of MenACWY-TT at Month 2		

The following subgroups, based on the country in which the subject is enrolled, will be used in analyses of demography, reactogenicity, and immunogenicity:

Subgroup order in Tables	Subgroup label in Tables
1	Australia
2	Canada
3	Czech Republic
4	Panama
5	South Africa
6	Turkey

The following subgroups, defined based on the number of doses of Prevenar 13 received before the study start (2 or 3 doses), will be used in analyses of demography, reactogenicity, and immunogenicity:

Subgroup order in Tables	Subgroup label in Tables	Subgroup definition for Footnote
1	2 doses of PCV13	Subjects received 2 doses of Prevenar 13 before the study start
2	3 doses of PCV13	Subjects received 3 doses of Prevenar 13 before the study start

3. OBJECTIVES

3.1. Primary Objectives

3.1.1. Exploratory Primary Objectives

- One (1) month after administration of meningococcal polysaccharide groups A, C, W-135, and Y tetanus toxoid conjugate vaccine (MenACWY-TT) in the ACWY1d vaccine group and the ACWY2d vaccine group:
 - To evaluate the immunogenicity of MenACWY-TT after administration of 1 dose in vaccine groups ACWY1d and ACWY2d or 2 doses in vaccine group ACWY2d with respect to serum bactericidal assay using rabbit complement to measure activity against *Neisseria meningitidis* groups A, C, W-135, and Y (rSBA-MenA, rSBA-MenC, rSBA-MenW-135, and rSBA-MenY) titers.
- One (1), 3, and 5 years after the last vaccination in the ACWY1d vaccine group and the ACWY2d vaccine group:
 - To evaluate the long-term persistence of the immune response induced by 1 or 2 doses of MenACWY-TT with respect to rSBA-MenA, rSBA-MenC, rSBA-MenW-135, and rSBA-MenY titers.

3.1.2. Confirmatory Primary Objectives

The confirmatory primary objectives will be assessed in a hierarchical manner according to the order presented below. The second confirmatory primary objective can only be considered as met if the statistical criteria for both that objective and the first confirmatory primary objective are met.

- To demonstrate the noninferiority of the immune response to MenACWY-TT when coadministered with Pfizer's 13-valent pneumococcal vaccine, Prevenar 13[®], versus MenACWY-TT given alone 1 month after vaccination.

Criterion for noninferiority of meningococcal groups A, C, W-135, and Y:

Noninferiority will be demonstrated for each group separately if the lower limit of the 2-sided standardized asymptotic 95% confidence interval (CI) for the group difference between the Co-ad group and the Pool1d group (Co-ad group minus Pool1d group) in the percentage of subjects with rSBA-MenA, rSBA-MenC, rSBA-MenW-135, and rSBA-MenY titers $\geq 1:8$ is greater than or equal to -10%.

- To demonstrate the noninferiority of the immune response to Prevenar 13 when coadministered with MenACWY-TT versus Prevenar 13 given alone 1 month after vaccination.

Criterion for noninferiority of pneumococcal serotypes 1, 3, 4, 5, 6A, 6B, 7F, 9V, 14, 18C, 19A, 19F, and 23F:

Noninferiority will be demonstrated for each serotype separately if the lower limit of the 95% CI of the geometric mean concentration (GMC) ratio between the Co-ad group and the PCV13 group (Co-ad group over PCV13 group) is above 0.5.

3.2. Secondary Objectives

One (1) month after administration of MenACWY-TT in the ACWY1d vaccine group and the ACWY2d vaccine group:

- To evaluate the immunogenicity of MenACWY-TT after administration of 1 dose in vaccine groups ACWY1d and ACWY2d or 2 doses in vaccine group ACWY2d with respect to serum bactericidal assay using human complement to measure activity against *N meningitidis* groups A, C, W-135, and Y (hSBA-MenA, hSBA-MenC, hSBA-MenW-135, and hSBA-MenY) titers in a subset of subjects.

One (1) month after administration of MenACWY-TT in the Co-ad vaccine group and the PCV13 vaccine group:

- To evaluate the immunogenicity of MenACWY-TT when administered as 1 dose with respect to rSBA-MenA, rSBA-MenC, rSBA-MenW-135, and rSBA-MenY titers.

One (1) month after administration of Prevenar 13 in the Co-ad vaccine group and the PCV13 vaccine group:

- To evaluate the immune response to Prevenar 13 coadministered with MenACWY-TT and Prevenar 13 administered alone with respect to antibody concentrations and titers against pneumococcal serotype-specific polysaccharides.

One (1), 3, and 5 years after the last vaccination in the ACWY1d vaccine group and the ACWY2d vaccine group:

- To evaluate the long-term persistence of the immune response induced by 1 or 2 doses of MenACWY-TT with respect to hSBA-MenA, hSBA-MenC, hSBA-MenW-135, and hSBA-MenY titers in a subset of subjects.

One (1), 3, and 5 years after the last vaccination in the Co-ad vaccine group and the PCV13 vaccine group:

- To evaluate the long-term persistence of the immune response induced by 1 dose of MenACWY-TT with respect to rSBA-MenA, rSBA-MenC, rSBA-MenW-135, and rSBA-MenY titers.

After each vaccine administration:

- To evaluate the safety and reactogenicity in terms of solicited events, unsolicited adverse events (AEs), serious adverse events (SAEs) and new-onset chronic illnesses (NOCIs) following each study vaccine dose.

One (1), 3, and 5 years after the last vaccination:

- To evaluate the occurrence of SAEs related to study vaccine administration and any event related to lack of vaccine efficacy (ie, meningococcal disease).

4. ENDPOINTS

4.1. Primary Endpoints

- Immunogenicity with respect to components of the study vaccines:

Percentages of subjects with rSBA-MenA, rSBA-MenC, rSBA-MenW-135, and rSBA-MenY titers $\geq 1:8$ one month after administration of 1 dose of MenACWY-TT in the ACWY1d, ACWY2d, and Co-ad vaccine groups and 1 month after administration of 2 doses in the ACWY2d vaccine group.

- Percentages of subjects with rSBA-MenA, rSBA-MenC, rSBA-MenW-135, and rSBA-MenY titers $\geq 1:8$ and $\geq 1:128$ and geometric mean titers (GMTs) at Years 1, 3, and 5 in the ACWY1d and ACWY2d vaccine groups.

- Anti-pneumococcal serotype 1, 3, 4, 5, 6A, 6B, 7F, 9V, 14, 18C, 19A, 19F, and 23F geometric mean antibody concentrations 1 month after administration of Prevenar 13 in the Co-ad and PCV13 vaccine groups.

4.2. Secondary Endpoints

- Immunogenicity with respect to components of the study vaccines:
 - Percentages of subjects with hSBA-MenA, hSBA-MenC, hSBA-MenW-135, and hSBA-MenY titers $\geq 1:4$ and $\geq 1:8$ and GMTs 1 month after administration of 1 dose of MenACWY-TT in a subset of subjects in the ACWY1d and ACWY2d vaccine groups and 1 month after administration of 2 doses in the ACWY2d vaccine group.
 - Percentages of subjects with rSBA-MenA, rSBA-MenC, rSBA-MenW-135, and rSBA-MenY titers $\geq 1:8$ and $\geq 1:128$ and GMTs 1 month after administration of 1 dose of MenACWY-TT in the PCV13 vaccine group.
 - Percentages of subjects with rSBA-MenA, rSBA-MenC, rSBA-MenW-135, and rSBA-MenY titers $\geq 1:128$ and GMTs 1 month after administration of 1 dose of MenACWY-TT in the ACWY1d, ACWY2d, and Co-ad vaccine groups.
 - Percentages of subjects with hSBA-MenA, hSBA-MenC, hSBA-MenW-135, and hSBA-MenY titers $\geq 1:4$ and $\geq 1:8$ and GMTs at Years 1, 3, and 5 in a subset of subjects in the ACWY1d and ACWY2d vaccine groups.
 - Percentages of subjects with rSBA-MenA, rSBA-MenC, rSBA-MenW-135, and rSBA-MenY titers $\geq 1:8$ and $\geq 1:128$ and GMTs at Years 1, 3, and 5 in the Co-ad and PCV13 vaccine groups.
 - Percentages of subjects with anti-pneumococcal serotype 1, 3, 4, 5, 6A, 6B, 7F, 9V, 14, 18C, 19A, 19F, and 23F antibody concentrations $\geq 0.15\mu\text{g/mL}$, $\geq 0.26\mu\text{g/mL}$, and $\geq 0.35\mu\text{g/mL}$ 1 month after administration of Prevenar 13 in the Co-ad and PCV13 vaccine groups.
 - Percentages of subjects with anti-pneumococcal serotype 1, 3, 4, 5, 6A, 6B, 7F, 9V, 14, 18C, 19A, 19F, and 23F OPA titers $\geq 1:8$ and GMTs 1 month after administration of Prevenar 13 in the Co-ad and PCV13 vaccine groups.
- Solicited local and general events:
 - Occurrence of each solicited local and general event within 4 days (Day 0 – Day 3) after each study vaccination.

- Unsolicited AEs:
 - Occurrence of unsolicited AEs within 31 days (Day 0 – Day 30) after any study vaccination, according to the Medical Dictionary for Regulatory Activities (MedDRA) classification.
- SAEs:
 - Occurrence of SAEs from Month 0 to Month 9.
- SAEs related to study vaccine administration:
 - Occurrence of SAEs related to study vaccine administration and any event related to lack of vaccine efficacy (ie, meningococcal disease) from the first receipt of study vaccine until study end.
- Occurrence of NOCIs:
 - Occurrence of NOCIs (eg, asthma, autoimmune disorders, type 1 diabetes, allergies) from Month 0 to Month 9.

5. STUDY POPULATIONS

Eight (8) cohorts are defined for the purpose of analyses. The definitions of the cohorts are given below:

5.1. Total Vaccinated Cohort

The total vaccinated cohort will include all subjects vaccinated with at least 1 dose of study vaccine.

The total vaccinated cohort analyses will be performed per vaccine actually administered at Dose 1.

5.2. According-to-protocol (ATP) Cohort for Safety

The ATP cohort for analysis of safety will include all vaccinated and eligible subjects:

- who meet all inclusion criteria and no exclusion criteria for the study.
- who have received at least 1 dose of study vaccine according to their random assignment.
- for whom administration site and route of study vaccine is known and according to protocol.
- who have not received the booster dose of Prevenar 13 outside the defined timeline (if administered, for vaccine groups ACWY1d and ACWY2d only).

- who have not received a vaccine forbidden in the protocol (subjects who received a vaccine not foreseen by the study protocol from 30 days before until 30 days after the administration of 1 [or more] of the study vaccine doses will be eliminated from the ATP cohort for safety if the vaccine not foreseen by the protocol was administered before the corresponding postvaccination blood sample).
- who have not received a meningococcal or pneumococcal vaccine not foreseen in the protocol, with the exception of the booster dose of Prevenar 13 in the ACWY1d and ACWY2d vaccine groups.

5.3. According-to-protocol Cohort for Immunogenicity after Dose 1

The ATP cohort for immunogenicity after Dose 1 will include all evaluable subjects (ie, those meeting all eligibility criteria, complying with the procedures defined in the protocol, and with no exclusion criteria during the study) from the ATP cohort for safety:

- who received all study vaccines at Month 0.
- for whom assay results are available with antibodies against at least 1 study vaccine antigen component at Visit 2.

Note: For the PCV13 vaccine group, subjects with an available blood sample at Visit 2 will be included in the ATP cohort for immunogenicity after Dose 1.

- who comply with the procedures and intervals defined in the protocol:
 - Date of birth to Vaccination 1 (Visit 1): 12 to 14 months.
 - Blood sample at Visit 1 to Vaccination 1 (Visit 1): at least 0 days (evaluation on case-by-case basis).
 - Vaccination 1 (Visit 1) to blood sample at Visit 2: 21 to 48 days.
- who have no concomitant infection that may influence immune response.
- who were not administered a vaccine not foreseen by the study protocol before the corresponding postvaccination blood sample.

5.4. According-to-protocol Cohort for Immunogenicity after Dose 2

The ATP cohort for immunogenicity after Dose 2 will include all evaluable subjects (ie, those meeting all eligibility criteria, complying with the procedures defined in the protocol, and with no exclusion criteria during the study) from the ACWY2d and PCV13 vaccine groups in the ATP cohort for safety:

- who received all study vaccines at Month 0 and Month 2.

- for whom assay results are available with antibodies against at least 1 study vaccine antigen component at Visit 4.
- who comply with the procedures and intervals defined in the protocol:
 - Date of birth to Vaccination 1 (Visit 1): 12 to 14 months.
 - Blood sample at Visit 1 to Vaccination 1 (Visit 1): at least 0 days (evaluation on case-by-case basis).
 - Vaccination 1 (Visit 1) to Vaccination 2 (Visit 3): 60 to 90 days.
 - Vaccination 2 (Visit 3) to blood sample at Visit 4: 21 to 48 days.
- who have no concomitant infection that may influence immune response.
- who were not administered a vaccine not foreseen by the study protocol before the post-Dose 2 blood sample.

5.5. Total Cohort Year X

The total cohort Year X will include all subjects who were both vaccinated and who return for Year X. “Year X” will refer to Year 1, Year 3, or Year 5.

5.6. According-to-protocol Cohort for Persistence at Year X

“Year X” will refer to Year 1, Year 3, or Year 5. The ATP cohort for persistence at Year X will include all subjects:

- who meet all eligibility criteria.
- who have received the complete primary vaccination series with MenACWY-TT according to their random assignment.
- who have assay results available for at least 1 antigen tested at the respective year (ie, Year X).
- who comply with the procedures and intervals defined in the protocol (refer to [Section 5.5](#) of the protocol).
- who did not receive a product leading to exclusion from an ATP analysis as listed in [Section 6.7.2](#) of the protocol.
- who did not present with a medical condition leading to exclusion from an ATP analysis as listed in [Section 6.8](#) of the protocol.

- who were not excluded from the ATP cohort for immunogenicity (after Dose 1 for the ACWY1d and Co-ad vaccine groups; after Dose 2 for the ACWY2d and PCV13 vaccine groups) and from the previous ATP cohorts for persistence (for Years 3 and 5 only) unless the reason for exclusion was either noncompliance with the protocol-defined serum sampling windows or lack of availability of immunogenicity results at the previous time point.

5.7. Adapted ATP Cohort

When presenting different time points, the adapted ATP cohort will be used to denote that, for each time point, the corresponding ATP cohort for immunogenicity/persistence has been used.

More specifically,

- the analyses on the pre- and post-Dose 1 time points will be based on the ATP cohort for immunogenicity after Dose 1.
- the analyses on the post-Dose 2 time point will be based on the ATP cohort for immunogenicity after Dose 2.
- the analysis on the Year 1, 3, and 5 time points will be based on the ATP cohort for persistence at Year 1, 3, and 5, respectively.

5.8. Adapted Total Cohort

When jointly presenting different time points, the adapted total cohort will be used to denote that, for each time point, the corresponding total cohort has been used.

More specifically,

- the analyses on the pre-Dose 1, post-Dose 1, and post-Dose 2 time points will be based on the total vaccinated cohort.
- the analyses on Year 1, 3, and 5 time points will be based on the total cohort Year 1, 3, and 5, respectively.

Note: The first analysis included the enzyme-linked immunosorbent assay (ELISA) results for MenACWY-TT up to Month 1 for the ACWY1d and Co-ad vaccine groups and up to Month 3 for the ACWY2d and PCV13 vaccine groups in order to analyze the immunogenicity endpoints related to MenACWY-TT as well as safety and reactogenicity for all vaccine groups up to Month 3. A second database cleaning was performed before the analysis of the immunogenicity endpoints related to PCV13 and the Month 9 safety follow-up. During this cleaning, GSK noticed that for some subjects concomitant vaccinations were reported after the DBF date for the first analysis, and these subjects need to be excluded from the ATP cohorts.

In order to exclude these subjects from the ATP cohorts and to maintain the possibility of regenerating the results published in the main study report, new elimination codes were introduced in the study. These new elimination codes R1 and R2 will be used for the reanalysis of immunogenicity related to MenACWY-TT and the new analysis will be included in an amendment to the main study report. They will also be used in the analysis of immunogenicity endpoints related to PCV13 and the Month 9 safety follow-up.

6. STATISTICAL METHODS

6.1. Analysis of Primary Vaccination

6.1.1. Demography

Demographic characteristics (age [in months, with range and standard deviation (SD)] at vaccination at Visit 1, sex, geographic ancestry, and ethnicity) of each study cohort will be tabulated per vaccine group.

The summary of number of doses of Prevenar 13 received before study start will also be tabulated.

The distribution of subjects enrolled among the study sites will be tabulated as a whole and per vaccine group.

The following demography analyses will also be performed overall, by country, and by the number of doses of Prevenar 13 received before the study (2 or 3 doses):

- Demographic characteristics (age [in months, with range and SD] at vaccination at Visit 1, sex, geographic ancestry, and ethnicity) will be tabulated for the ATP cohort for immunogenicity.
- Summary of subjects enrolled into the study and excluded from ATP analyses along with reasons for exclusion.
- Number of subjects vaccinated, withdrawn, and completed with reasons for withdrawal.

6.1.2. Analysis of Immunogenicity

The primary analysis of immunogenicity will be performed on the adapted ATP cohort. At the post-Dose 1 time point, the analysis will be done on the ATP cohort for immunogenicity after Dose 1. At the post-Dose 2 time point, the analysis will be done on the ATP cohort for immunogenicity after Dose 2.

A second analysis on the total vaccinated cohort will be performed to support the ATP analysis if:

- the percentage of subjects enrolled in groups Co-ad or ACWY1d with serological results at Visit 2 excluded from the ATP cohort for immunogenicity after Dose 1 is more than 5% or
- the percentage of subjects enrolled in groups ACWY2d or PCV13 with serological results at Visit 4 excluded from the ATP cohort for immunogenicity after Dose 2 is more than 5%.

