**CONFIDENTIAL**

C0921003 (MENACWY-TT-104,116892)

Protocol Amendment 3, 09 May 2018

---

It is the investigator's responsibility to ensure that the intervals between visits are strictly followed. These intervals determine each subject's evaluability in the according-to-protocol (ATP) analyses.

The intervals between study visits are presented in Table 7 for the ACWY1d and Co-ad groups and in Table 8 for the ACWY2d and PCV-13 groups. Visits refer to the day of vaccination.

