**Table 8. Intervals Between Study Visits for Groups ACWY2d and PCV-13**

Interval	Optimal length of interval	Allowed interval 
Date of birth → first vaccination	12-14 months	12-14 months
Visit 1 → Visit 2	30 days	21 days - 48 days
Visit 1 → Visit 3	60 days	60 days - 90 days
Visit 3 → Visit 4	30 days	21 days - 48 days
Visit 1 → Phone contact	270 days	270 - 300 days
Visit 3 → Visit 5	12 months	44 - 60 weeks
Visit 3 → Visit 6	36 months	148 - 164 weeks
Visit 3 → Visit 7	60 months	252 - 268 weeks

 Whenever possible the investigator should arrange study visits within this interval.

 Subjects will not be eligible for inclusion in the ATP cohort for analysis of immunogenicity or persistence Year 1, 3 or 5 if they make the study visit outside this interval (see [Section 10.4](#) for more details). If a subject returns for the Visit 2 blood draw prior to completion of the 31-day safety follow-up period, the subject should continue to record this information on the diary card until 31 days post-vaccination and mail the diary card to the site. The investigator will make an attempt to obtain this information as soon as possible after the 31-day follow-up period if it is not mailed in.

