### 10.6.2. Analysis of Immunogenicity

The primary analysis of immunogenicity will be performed on the ATP cohort for immunogenicity. At post dose 1, the analysis will be done on the ATP cohort for immunogenicity post dose 1. At post dose 2, the analysis will be done on the ATP cohort for immunogenicity post dose 2.

A second analysis on the Total Vaccinated Cohort will be performed to support the ATP analysis if:

- the percentage of subjects enrolled in groups Co-ad or ACWY1d with serological results at Visit 2 excluded from the ATP cohort for immunogenicity post dose 1 is more than 5% or,
- the percentage of subjects enrolled in groups ACWY2d or PCV-13 with serological results at Visit 4 excluded from the ATP cohort for immunogenicity post dose 2 is more than 5%.

In addition to the overall analyses, the immunogenicity analyses on the ATP cohort for immunogenicity post dose 1 and on the ATP cohort for immunogenicity post dose 2 will be performed by country and by the number of doses of *Prevenar 13* received before the study (2 or 3 doses).

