6.1.2.2. Between Vaccine Groups

Confirmatory Primary Objectives

Noninferiority of MenACWY-TT when coadministered with Prevenar 13 versus MenACWY-TT given alone 1 month after vaccination.

- Two (2)-sided standardized asymptotic 95% CI of the vaccine group difference between the Co-ad and the Pool1d vaccine groups (Co-ad vaccine group minus Pool1d vaccine group) will be computed for the percentage of subjects with rSBA-MenA, rSBA-MenC, rSBA-MenW-135, and rSBA-MenY titer $\geq 1:8$ (Visit 2).

It can be concluded (for each meningococcal group separately) that coadministration of MenACWY-TT and Prevenar 13 is noninferior to administration of MenACWY-TT alone if the lower limit of the CI of the difference is greater than or equal to -10%.

Noninferiority of Prevenar 13 when coadministered with MenACWY-TT versus Prevenar 13 given alone 1 month after vaccination.

- 95% CI of the GMC ratio between the Co-ad and the PCV13 vaccine groups (Co-ad vaccine group over PCV13 vaccine group) will be computed for pneumococcal serotypes 1, 3, 4, 5, 6A, 6B, 7F, 9V, 14, 18C, 19A, 19F, and 23F (Visit 2). This will be performed using an analysis of covariance (ANCOVA) model on the \log_{10} transformation of the concentrations using the prevaccination \log_{10} transformation of the concentrations, the country, the number of doses of Prevenar 13 received before the study (2 or 3 doses), and the vaccine group as covariates.

It will be concluded (for each serotype separately) that coadministration of Prevenar 13 and MenACWY-TT is noninferior to administration of Prevenar 13 alone if the lower limit of the CI of the GMC ratio is above 0.5.

Exploratory Analysis

An exploratory evaluation of the comparability of the immune response to each pneumococcal serotype at 1 month after administration of Prevenar 13 will be done through:

- Computation of the asymptotic standardized 95% CI on the difference between the percentages of subjects with antibody concentrations and OPA titers above proposed cutoffs between the vaccine groups Co-ad and (minus) PCV13 (Visit 2).

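### The 5% trigger for the supportive Total Vaccinated Cohort analysis checks ACWY2d and PCV-13 at Visit 4, but both confirmatory tests use those groups at Visit 2

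*SAP*

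**What the plan says.** Protocol 10.6.2 and SAP 6.1.2 give the same two-part rule. The Total Vaccinated Cohort analysis is added if more than 5% of subjects are affected in either part:

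- Co-ad and ACWY1d: those "enrolled in groups Co-ad or ACWY1d with serological results at Visit 2 excluded from the ATP cohort for immunogenicity post dose 1" (Protocol 10.6.2).
- ACWY2d and PCV-13: those "enrolled in groups ACWY2d or PCV13 with serological results at Visit 4 excluded from the ATP cohort for immunogenicity after Dose 2" (SAP 6.1.2).

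For the analysis itself, SAP 6.1.2 states: "At the post-Dose 1 time point, the analysis will be done on the ATP cohort for immunogenicity after Dose 1". SAP 6.1.2.2 places both confirmatory tests at Visit 2. Test 1 compares Co-ad with Pool1d on the percentage with rSBA titres of at least 1:8. Pool1d is ACWY1d plus ACWY2d after the first dose (Protocol 1.2.2). Test 2 uses the "95% CI of the GMC ratio between the Co-ad and the PCV13 vaccine groups" for each of the 13 serotypes.

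No other section adds a Visit 2 check for ACWY2d or PCV-13.

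**The concern.** A trigger of this kind should count exclusions from the cohort on which the test is run. Here, two of the groups in the confirmatory tests are judged on a later visit and a different cohort. PCV-13 is the clearest case: Protocol Table 11 lists only rSBA for it at Visit 4, while the test 2 endpoint is pneumococcal ELISA, measured at Visits 1 and 2.

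The plan's other triggers do not split the groups. The safety rule (SAP 6.1.3) covers any vaccine group, and the persistence rule (SAP 6.2.2) covers any group at any time point. The same split by last primary dose appears in the persistence cohort definition (SAP 5.6), where it makes sense. It does not suit a test at Visit 2.

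The Total Vaccinated Cohort run is the only planned non-ATP analysis of the two non-inferiority tests. Whether it is done depends partly on the wrong exclusions.

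**Working it through.** **1. The plan's own figures.** The global power in Protocol 10.3 is 100% minus the sum of the individual betas. Test 1: 0.01 + 0.12 + 0.01 + 0.12 = 0.26%. Test 2: ten serotypes at 0.01, plus 0.15 + 0.02 + 0.16 = 0.43%. The total is 0.69%, so power is 99.31%, as stated. Recomputing the larger test 2 betas at 160 per group gives 0.153% (6B), 0.017% (14) and 0.162% (23F). A score-test approximation gives 0.119% for a 97.3% rate at 160 versus 320 (stated 0.12%); exact enumeration gives 0.195%, which is immaterial here. None of this depends on the trigger.

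**2. Reach of the Visit 2 check, at planned evaluable numbers.**
- Test 1: 160 Co-ad + 160 ACWY1d = 320 of 480 subjects. The other 160 (ACWY2d) are half of the control.
- Test 2: 160 Co-ad of 320. The other 160 (PCV-13) are the whole control.
- Crossing 5% takes 9 exclusions of 160, or 11 of 200.

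**3. Route A: a Visit 2 result but no Visit 4 result.** Let e be the share excluded at Visit 2 and m the share with no Visit 4 result. I read the Visit 4 percentage as taken among subjects with a Visit 4 result. If exclusion and loss are independent, the rate is e(1 − m)/(1 − m) = e, so nothing is lost. Assumed example: 20 of 200 excluded (10%). With m = 10% the rule reads 18 of 180; with m = 20% it reads 16 of 160. Both are 10%.

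A gap therefore needs loss to be related to exclusion. With 20 of 200 lost, the rule stays silent if at most 9 of the remaining 180 are excluded (9/180 = 5.0%, not above 5%):
- 20 excluded: at least 11 of them must be among the 20 lost, against 20 × 0.10 = 2 expected under independence.
- 11 excluded (5.5%): 2 among the 20 lost is enough, against 20 × 0.055 = 1.1 expected.

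So the route needs strong dependence when exclusions are common and little when they sit near 5%. These counts are assumptions; the documents give none.

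**4. Route B: an out-of-window Visit 2 sample.** The interval list in SAP 5.4 includes "Vaccination 2 (Visit 3) to blood sample at Visit 4: 21 to 48 days" but no Visit 2 window. Read literally, 11, 20 or 40 of 200 subjects (5.5%, 10%, 20%, assumed) who missed only the Visit 2 window would register as 0% at Visit 4. But the opening of SAP 5.4 requires subjects to be "complying with the procedures defined in the protocol, and with no exclusion criteria during the study". Protocol 5.5 says that visit intervals determine "evaluability in the according-to-protocol (ATP) analyses", and footnote 2 of Protocol Table 8 says of visits outside the interval: "Subjects will not be eligible for inclusion in the ATP cohort for analysis of immunogenicity". Read that way, the same subjects also leave the post-Dose-2 cohort and are counted if they have a Visit 4 result.

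**5. The opposite error.** The post-Dose-2 cohort also requires the second vaccination, the 60 to 90 day interval and the Visit 4 window. Failing the 60 to 90 day interval or the Visit 4 window can fire the rule without bearing on a Visit 2 test.

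**6. Possible effect on the estimates (assumed restorations).**
- Test 2, unadjusted, true ratio 1, SD 0.549, 160 per group: lower limit = 10^(−1.967 × 0.549 × √(2/160)) = 0.757. If 2% of PCV-13 are restored with two-fold higher GMC, the ratio is multiplied by 2^(−0.02) = 0.986, giving 0.747. For 10%, 2^(−0.10) = 0.933, giving 0.707. The criterion is 0.5.
- Test 1, 97.3% response, Pool1d of 400, restored ACWY2d subjects all responders: for 2% of ACWY2d, (0.973 × 396 + 4)/400 − 0.973 = 0.00027, or 0.03 points. For 10%, (0.973 × 380 + 20)/400 − 0.973 = 0.00135, or 0.14 points. The margin is 10 points.

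**The case against.** The strongest reply is that the rule already catches most of what matters. The two parts are joined by an or, so one group over 5% is enough. Co-ad, which is in both tests, is checked at Visit 2. Both immunogenicity cohorts are drawn from the ATP cohort for safety, so eligibility, wrong-vaccine, route and forbidden-vaccine exclusions reach the Visit 4 count whenever a Visit 4 result exists. The extra post-Dose-2 criteria may make the rule fire more readily. All of this stands, and it makes the gap partial. It does not make the rule fit the tests.

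A second reply concerns timing. PCV-13 has only pneumococcal assays at Visit 2 (Protocol Table 11), and SAP 9 says that those data were not available at the first analysis. A Visit 2 check on PCV-13 results was not possible then. That also stands, but the pneumococcal endpoints belong to the second analysis (SAP 8.1), when the check can be made.

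A third is that SAP 6.1.1 already tabulates exclusions with reasons. That would show a problem at Visit 2, but it triggers nothing.

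A reader might infer that the Total Vaccinated Cohort run is the only planned look at either test on another cohort. That goes too far: the note in SAP 5.8 plans a reanalysis of MenACWY-TT immunogenicity after new elimination codes. It is still an ATP analysis.

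**Conclusion.** The mismatch is plain in both documents and no other section repairs it. It affects only whether a supportive analysis is run. The primary ATP analysis, alpha and power do not change, and in the assumed examples the estimates move little against their margins. Severity is minor.

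Three stronger readings are tempting and not supported:

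- That Visit 2 exclusions in ACWY2d and PCV-13 go uncounted altogether. Those shared with the post-Dose-2 cohort are counted when a Visit 4 result exists.
- That ordinary dropout opens a gap of known size, or lowers the chance of triggering by a known amount. Under independence the two rates are equal. The 20% in Protocol 10.3 combines withdrawal and non-evaluability and is not a rate of missing Visit 4 results. The documents give no exclusion rates.
- That the non-inferiority conclusions are unsafe. Nothing in the documents shows this.

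The conclusion rests on the text of the rule. Only the sizes depend on assumed counts, on reading the percentage among subjects with a Visit 4 result, and, for out-of-window samples, on a literal reading of SAP 5.4.

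**What to change.** Preferred: run the Total Vaccinated Cohort analysis of both Visit 2 confirmatory tests in any case, and report it as supportive.

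Alternative: apply the 5% rule to all four groups at Visit 2 against the post-Dose-1 cohort, assessing PCV-13 at the second analysis, when its Visit 2 results exist. Keep the Visit 4 check against the post-Dose-2 cohort for the Visit 4 analyses.

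Under either option, state whether an out-of-window Visit 2 sample removes a subject from the post-Dose-2 cohort, so that Protocol Table 8 footnote 2 and SAP 5.4 agree.

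The cost is one extra run of existing programs on another cohort flag and a short SAP note. It must be labelled post hoc, because the SAP document history records that the Month 0 to Month 9 analyses had already been performed.
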